Cohort 2: In another 3 patients, the dose of CPI-613 for the 3-weeks-on-1-week-off treatment cycles will be as determined from Cohort 1. These patients will also be treated with the 5 daily doses of CPI-613 during the pre-Cycle 1 week. The dose of CPI-613 for the pre-Cycle 1 week will be 1,200 mg/m²/day, which has previously been established to be the weekly MTD (see Section 6.1.2). If none of these 3 patients develop a DLT, the study can move onto Cohort 3.

However, if a DLT is observed in a patient (whether it is the 1st, 2nd or 3rd of the 3 intended patients), the number of patients in this cohort will be expanded to a maximum of 6 patients. If no DLT is observed in another patient out of a maximum of 6 patients, the study will move onto Sub-Cohort 2 (see below). However, if a DLT is observed in 2 patients, no additional patients will be treated at 1,200 mg/m²/day during the pre-Cycle 1 week even though the total number of patients at this cohort is as few as 2. The dose level of 1,200 mg/m²/day during the pre-Cycle 1 week, which induces a DLT in 2 or more patients, is considered to be above the MTD for the pre-Cycle 1 week. In this case, the dose of CPI-613 for the pre-Cycle 1 week in subsequent patients in this trial will be 600 mg/m²/day (or 3,000 mg/m²/week, equivalent to the MTD when given as a single dose).

Sub-Cohort 2: Sub-Cohort 2 is activated only if 1 out of 6 patients exhibits DLT in Cohort 2. There are 3 patients in this sub-cohort, the dose of CPI-613 for the 3-weeks-on-1-week-off treatment cycles will be as determined from Cohort 1. These patients will also be treated with the 5 daily doses of CPI-613

Comprehensive Cancer Center of Wake Forest University
A Pilot Study: Open-Label Clinical Trial of CPI-613 in Patients with Advanced Bile Duct
Cancers
CCCWFU # 59212

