during the pre-Cycle 1 week. The dose of CPI-613 for the pre-Cycle 1 week will be 1,700 mg/m²/day. If none of these 3 patients develop a DLT, the study can move onto Cohort 3. However, if a DLT is observed in a patient (whether it is the first, second or third of the 3 intended patients), the number of patients in this cohort will be expanded to a maximum of 6 patients. If no DLT is observed in another patient out of a maximum of 6 patients, the study will move onto Cohort 3. However, if a DLT is observed in 2 patients, no additional patients will be treated at 1,700 mg/m²/day during the pre-Cycle 1 week even though the total number of patients at this sub-cohort is as few as 2. The dose level of 1,700 mg/m²/day during the pre-Cycle 1 week, which induces a DLT in 2 or more patients, is considered to be above the MTD for the pre-Cycle 1 week. In this case, the dose of CPI-613 for the pre-Cycle 1 week in subsequent patients in this trial will be 600 mg/m²/day (or 3,000 mg/m²/week, equivalent to the MTD when given as a single dose).

Cohort 3: This cohort will be performed only if DLT is observed in Cohort 2, or DLT is observed in 1 or less patients in Sub-Cohort 2. There are 3 patients in this cohort, and the dose of CPI-613 for the 3-weeks-on-1-week-off treatment cycles will be as determined from Cohort 1. The dose for the 5 daily IV infusions during the pre-Cycle 1 week will be 2,300 mg/m²/day. If none of these 3 patients develop a DLT, the study can move onto Cohort 4. However, if a DLT is observed in a patient (whether it is the 1st, 2nd or 3rd of the 3 intended patients), the number of patients in this cohort will be expanded to a maximum of 6 patients. If no DLT is observed in another patient out of a maximum of 6 patients, the study will move onto Cohort 4. However, if a DLT is observed in 2 patients, no additional patients will be treated at 2,300 mg/m²/day during the pre-Cycle 1 week even though the total number of patients at this sub-cohort is as few as 2. The dose level of 2,300 mg/m²/day during the pre-Cycle 1 week, which induces a DLT in 2 or more patients, is considered to be above the MTD for the pre-Cycle 1 week. In this case, the dose of CPI-613 for the pre-Cycle 1 week in subsequent patients in this trial will be 1,700 mg/m²/day.

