Cohort 4: This cohort will be performed only if DLT is observed in 1 or less patients in Cohort 3. There are 3 patients in this cohort, and the dose of CPI-613 for the 3-weeks-on-1-week-off treatment cycles will be as determined from Cohort 1. The dose for the 5 daily IV infusions during the pre-Cycle 1 week will be 3,000 mg/m²/day. If none of these 3 patients develop a DLT, the study can move onto Cohort 5. However, if a DLT is observed in a patient (whether it is the first, second or third of the 3 intended patients), the number of patients in this cohort will be expanded to a maximum of 6 patients. If no DLT is observed in another patient out of a maximum of 6 patients, the study will move onto Cohort 5. However, if a DLT is observed in 2 patients, no additional patients will be treated at 3,000 mg/m²/day during the pre-Cycle 1 week even though the total number of patients at this cohort is as few as 2. The dose level of 3,000

Comprehensive Cancer Center of Wake Forest University
A Pilot Study: Open-Label Clinical Trial of CPI-613 in Patients with Advanced Bile Duct
Cancers
CCCWFU # 59212

mg/m²/day during the pre-Cycle 1 week, which induces a DLT in 2 or more patients, is considered to be above the MTD for the pre-Cycle 1 week. In this case, the dose of CPI-613 for the pre-Cycle 1 week in subsequent patients in this trial will be 2,300 mg/m²/day

Cohort 5: This cohort is performed once the dose of CPI-613 for the 3-weeks-on-1-week-off treatment cycles has been determined from Cohort 1, and once the dose of CPI-613 for the pre-Cycle 1 week has been determined from Cohort 2-4. There are 10 patients in this cohort. These patients will be treated with CPI-613 for 5 days during the pre-Cycle 1 week at doses as determined from Cohorts 2-4, and the dose of CPI-613 for the 3-weeks-on-1-week-off treatment cycles will be as determined from Cohort 1.

6.1.2 *Justification of the Dose*

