For adverse events unrelated to serum creatinine elevation or reduction in renal function but are possibly related to CPI-613, the occurrence of Grade 1 toxicity does not generally require dose modification for subsequent doses for that patient. However, if Grade 2 toxicity (other than alopecia and nausea) probably related to CPI-613 develops, treatment is to be withheld and can resume only after the Grade 2 toxicity has been reduced to Grade 1 or below, and the dose level for subsequent doses for that patient will be reduced by 25% of the dose at which such Grade 2 toxicity occurs. Grade 2 alopecia and nausea do not require withholding treatment or dose reduction. If Grade 3 or 4 toxicity probably related to CPI-613 develops, dosing of CPI-613 of that patient will be withheld and the patient shall be monitored for recovery from, and reversibility of, such Grade 3 or 4 toxicity. To resume treatment with CPI-613 for a patient who has had CPI-613-related Grade 3 or 4 toxicity, the Grade 3 or 4 toxicity must be reduced to Grade 1 or below, and the dose level for subsequent doses for that patient will be reduced to 50% of the dose at which such Grade 3 or 4 toxicity occurs.

For adverse events related to creatinine elevation or reduction in renal function that are possibly related to CPI-613, dosing of the patient will be withheld even if the severity level is Grade 2 or above. Treatment can resume only after the toxicity has been reduced to Grade 1. The dose level for subsequent doses for that patient will be reduced by 15% if the severity level is of Grade 1, by 25% for Grade 2 toxicity, and by 50% for Grade 3 or 4 toxicity.

Furthermore, if the toxicity possibly related to CPI-613 is acute renal failure and the severity level is Grade 3 or 4, further patient enrollment will be temporarily suspended in order to enable assessment of the following aspects of the trial and implementation of corrective measures or protocol amendment, and if necessary:

- compliance of the study sites and investigators to the study protocol
- evaluation of the appropriateness of the procedures for monitoring renal function

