8.0 ADVERSE EVENTS LIST AND REPORTING REQUIREMENTS

8.1 Adverse Event Characteristics

- **CTCAE term (AE description) and grade:** The CTEP Active Version of the NCI Common Terminology Criteria for Adverse Events (CTCAE 4.0) will be utilized for AE reporting. The CTEP Active Version of the CTCAE is identified and located on the CTEP website at http://ctep.cancer.gov/protocolDevelopment/electronic_applications/ctc.htm. All appropriate treatment areas should have access to a copy of the CTEP Active Version of CTCAE.
- **‘Expectedness’:** AEs can be ‘Unexpected’ or ‘Expected’ (see Section 7.1 above) for expedited reporting purposes only.
- **Attribution of the AE:**
 - Definite – The AE *is clearly related* to the study treatment.
 - Probable – The AE *is likely related* to the study treatment.
 - Possible – The AE *may be related* to the study treatment.
 - Unlikely – The AE *is doubtfully related* to the study treatment.
 - Unrelated – The AE *is clearly NOT related* to the study treatment.

List of Adverse Events to be Reported:

Comprehensive Cancer Center of Wake Forest University
A Pilot Study: Open-Label Clinical Trial of CPI-613 in Patients with Advanced Bile Duct
Cancers
CCCWFU # 59212

*Abdominal pain
Alkaline phosphatase
ALT (SGPT)
Anorexia
AST (SGOT)
Bilirubin (hyperbilirubinemia)
Calcium (hypercalcemia, hypocalcemia)
*Creatinine
*Diarrhea
Flushing
Hemoglobin (anemia)
*Injection site Reaction
Leukocytes
Lymphopenia
*Nausea
Neutrophils (neutropenia)
Platelets (thrombocytopenia)
Potassium
Sodium
*Vomiting

All grade 3, 4, 5 adverse events should be reported on flowsheets and in ORIS regardless of whether they are on this list.

Asterisk (*) denotes expected Adverse Events.

All Serious Adverse Events (SAEs) which are Possibly, Probably or Definitely Related to CPI-613, and Unexpected are required to be reported to Cornerstone Pharmaceuticals via the provided SAE Reporting Form within 7 days. All completed forms must be sent to [name] at Cornerstone. Cornerstone will submit any applicable SAEs to the FDA.

SAE reports must be submitted to Cornerstone by fax or email to the following address:

Department of Regulatory and Clinical Affairs
Cornerstone Pharmaceuticals, Inc.
[name]
[name]
[contact]
Telefax: [contact] Email: [contact]

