8.3 WFUHS IRB AE Reporting Requirements

Any unanticipated problems involving risks to subjects or others and adverse events shall be promptly reported to the IRB, according to institutional policy. Reporting to the IRB is required regardless of the funding source, study sponsor, or whether the event involves an investigational or marketed drug, biologic or device. Reportable events are not limited to physical injury, but include psychological, economic and social harm. Reportable events may arise as a result of drugs, biological agents, devices, procedures or other interventions, or as a result of questionnaires, surveys, observations or other interactions with research subjects.

All members of the research team are responsible for the appropriate reporting to the IRB and other applicable parties of unanticipated problems involving risk to subjects or others. The Principal Investigator, however, is ultimately responsible for ensuring the prompt reporting of unanticipated problems involving risk to subjects or others to the IRB. The Principal Investigator is also responsible for ensuring that all reported unanticipated risks to subjects and others which they receive are reviewed to determine whether the report represents a change in the risks and/or benefits to study participants, and whether any changes in the informed consent, protocol or other study-related documents are required.

Any unanticipated problems involving risks to subjects or others occurring at a site where the study has been approved by the WFUHS IRB (internal events) must be reported to the WFUHS IRB within 7 calendar days of the investigator or other members of the study team becoming aware of the event.

Any unanticipated problems involving risks to subjects or others occurring at another site conducting the same study that has been approved by the WFUHS IRB (external events) must be reported to the WFUHS IRB within 7 calendar days of the investigator or other members of the study team becoming aware of the event.

Any event, incident, experience, or outcome that alters the risk versus potential benefit of the research and as a result warrants a substantive change in the research protocol or informed consent process/document in order to insure the

Comprehensive Cancer Center of Wake Forest University
A Pilot Study: Open-Label Clinical Trial of CPI-613 in Patients with Advanced Bile Duct
Cancers
CCCWFU # 59212

safety, rights or welfare of research subjects.

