even though the total number of patients at this cohort is as few as 2. The dose level of 3,000 mg/m²/day during the pre-Cycle 1 week, which induces a DLT in 2 or more patients, is considered to be above the MTD for the pre-Cycle 1 week. In this case, the dose of CPI-613 for the pre-Cycle 1 week in subsequent patients in this trial will be 2,300 mg/m²/day

Cohort 5: This cohort is performed once the dose of CPI-613 for the 3-weeks-on-1-week-off treatment cycles has been determined from Cohort 1, and once the dose of CPI-613 for the pre-Cycle 1 week has been determined from Cohort 2-4. There are 10 patients in this cohort. These patients will be treated with CPI-613 for 5 days during the pre-Cycle 1 week at doses as determined from Cohorts 2-4, and the dose of CPI-613 for the 3-weeks-on-1-week-off treatment cycles will be as determined from Cohort 1.

As can be seen by the above scheme there are several possible scenarios that could occur in order to determine the dose for the 10 patients to be evaluated in the pilot trial. Once the above procedure is completed we will then enroll 10 patients at the determined dose.

Accrual Rate

We anticipate accruing one patient per month for this protocol. Since the dose escalation procedure described above may involve a variable number of patients (at least 6 but possibly more) we cannot be certain the entire length of accrual for this protocol. However, we do anticipate that the total number of patients in this protocol will be between 16-40 (with 16-22 being the most likely range). Thus, we anticipate that we will reach the target sample size of 10 patients treated at MTD within two years. A minimum of 16 patients to a maximum of 40 patients will be accrued to the study, with the first 6-30 being evaluated for toxicity in a dose-escalated manner for determining the MTD, and the remaining 10 used in the analytic sample.

Proposed Analyses

The analyses for this protocol will be primarily descriptive. With a sample size of 10 treated at MTD, we do not expect to see statistically significant effects for the outcomes of interest, however this data will provide useful preliminary data on the overall safety and efficacy of CPI-613 and provide useful data to predict the variability and likely effect sizes for these outcomes.

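### Cohort 5, the 10-patient analysis and toxicity sample, has no DLT count that requires a review, although every escalation level stops at 2 DLTs in at most 6 patients

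*Combined protocol and SAP*

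**What the plan says.** Section 6.1.1, repeated in Section 9.0, defines five escalation steps: Cohorts 1, 2, Sub-Cohort 2, 3 and 4. Each starts with 3 patients, grows to at most 6 after one DLT, and closes its dose at the second DLT. Cohort 4 is typical: "However, if a DLT is observed in 2 patients, no additional patients will be treated at 3,000" mg/m²/day in the pre-Cycle 1 week.

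The Cohort 5 paragraph is different: "There are 10 patients in this cohort. These patients will be treated with CPI-613 for 5 days during the pre-Cycle 1 week", at the doses found earlier. It has no DLT count, pause or step-down. Section 9.0 adds only "Once the above procedure is completed we will then enroll 10 patients at the determined dose", and says that toxicities in these 10 will be examined by grade. The DLT window, through Cycle 1, is set for cohorts in the dose-escalation scheme. Section 9.0 also separates the first 6-30 patients, assessed for toxicity to find the MTD, from the last 10, who form the analysis sample.

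Safeguards that do apply to Cohort 5:

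- Section 6.2: dosing is held and then reduced for the affected patient. For Grade 3 or 4 acute renal failure possibly related to the drug, "further patient enrollment will be temporarily suspended in order to enable assessment".
- Section 6.3: the sponsor may terminate the trial.
- Section 8.1: "All grade 3, 4, 5 adverse events should be reported on flowsheets and in ORIS regardless of whether they are on this list". Serious events that are related and unexpected go to the drug sponsor within 7 days.
- Section 8.3: unanticipated problems "must be reported to the WFUHS IRB within 7 calendar days of the investigator" or study team becoming aware. A closing clause covers any outcome that alters risk against benefit enough to warrant a substantive change to the protocol or consent.
- Section 8.2 and Appendix B: the STRC reviews unexpected Grade 4 and all Grade 5 events and may suspend the trial.

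**The concern.** Safety is a primary outcome, and these 10 patients are the ones described as treated at the MTD. Yet the numerical rule that governs each escalation level ends just before them. A level can clear on 0/3 or 1/6 by chance and still be too toxic, so clearing it does not make a count unnecessary afterwards. Cohort 5 could pass the number that closed every earlier level without anyone being obliged to look.

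On some paths Cohort 5 is also the first group in this trial to receive its pre-Cycle 1 dose. After 0/3 DLTs in Cohort 2, "If none of these 3 patients develop a DLT, the study can move onto Cohort 3", which is at 2,300 mg/m²/day. If Cohort 3 then fails, the dose "for the pre-Cycle 1 week in subsequent patients in this trial will be 1,700" mg/m²/day. Sub-Cohort 2, the only cohort assigned that dose, will not have opened. The 600 mg/m²/day fallback is likewise untested here.

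**Working it through.** **Which events escape mandatory review.** The Appendix B table marks Grade 1-3 events and expected Grade 4 events as not requiring an STRC report, and the text also leaves out routinely experienced events. Sponsor reporting under 8.1 needs a serious event that is both related and unexpected. Six events are starred as expected: abdominal pain, creatinine, diarrhea, injection site reaction, nausea and vomiting. A run of related Grade 3 events of these types would be recorded, but neither rule would send it to the STRC or the sponsor. The STRC form does ask whether severity was unexpected, so a Grade 4 event of a starred type may still be reported.

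**The plan's own figures.** The stated accrual range reproduces as 3 + 3 + 10 = 16 and 5 × 6 + 10 = 40, with Cohort 5 fixed at 10. The plan states no operating characteristic for Cohort 5 toxicity.

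**Inputs.** From 6.1.1: 3 patients expanding to 6, stop at 2 DLTs, Cohort 5 of 10. From 9.0: accrual of one patient per month. Assumed: a true DLT rate p of 10% to 50%, constant and independent between patients.

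**Formulas.**

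1. A level, once reached, clears with probability (1-p)³ + 3p(1-p)⁵. At p = 0.3: 0.343 + 0.151 = 0.494.
2. The plan's own count carried into Cohort 5 (2 within the first 6) pauses with probability 1 - (1-p)⁶ - 6p(1-p)⁵. At p = 0.3: 1 - 0.118 - 0.303 = 0.580 (unrounded terms).
3. Limits of 3 within 7-8 and 4 within 9-10 add 6p(1-p)⁵ × [p² + 2p³(1-p)] + (1-p)⁶p⁴. At p = 0.3: 0.303 × 0.128 + 0.118 × 0.0081 = 0.040, giving 0.619.

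| Assumed true DLT rate | 10% | 20% | 30% | 40% | 50% |
|---|---|---|---|---|---|
| Level clears once reached | 0.906 | 0.709 | 0.494 | 0.309 | 0.172 |
| Pause, 2 within first 6 only | 0.114 | 0.345 | 0.580 | 0.767 | 0.891 |
| Pause, full rule | 0.118 | 0.366 | 0.619 | 0.812 | 0.927 |
| Clears one level, then pauses (full rule) | 0.107 | 0.259 | 0.306 | 0.251 | 0.159 |
| Mean treated before review, full rule, one further patient enrolled | 9.48 | 8.36 | 7.11 | 5.97 | 5.05 |

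The comparison for the last row is 10, if no other safeguard acts. One further patient is a reasonable allowance: the DLT window is about five weeks (one week plus a four-week cycle) and accrual is monthly. For the 2-in-6 count alone, the means are 9.37/8.03/6.55/5.23/4.19 with none further and 9.60/8.72/7.71/6.77/5.97 with two.

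**Why patients 7-10 need a limit.** With the 2-in-6 count alone, 3 or more DLTs in 10 pass without a trigger with probability 0.08/0.12/0.11 at 20/30/40%. The later limits remove 0.02/0.04/0.05 of that. What remains is exactly 3 in 10, below one third; the limits themselves are 2/6 = 0.33, 3/8 = 0.375 and 4/10 = 0.40.

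**The 1,700 mg/m²/day path.** Its probability is (1-p2)³ × (1 - P(clear; p3)), where p2 and p3 are the Cohort 2 and Cohort 3 rates. With p2 = 10%: 0.729 × 0.291 = 0.21 at p3 = 20%, 0.729 × 0.506 = 0.37 at 30%, and 0.729 × 0.691 = 0.50 at 40%. Taking p2 from 5% to 20% widens the range to 0.15-0.59. This uses the Cohort 2 rule that 0/3 leads to Cohort 3. The Cohort 3 paragraph literally opens that cohort only if a DLT is seen in Cohort 2 (or at most one in Sub-Cohort 2). That conflicts with the Cohort 2 rule and looks like a typing error.

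**The case against.** A reader might infer that Cohort 5 has no safety brake and that all 10 patients would be treated whatever happened. The documents do not support this. The STRC can suspend the trial, the sponsor can end it, renal failure suspends enrolment, and the closing clause of 8.3 could take in a run of DLTs. Each patient with a probably related Grade 3 or 4 toxicity is held and resumes, if at all, at half dose. What is missing is a number that makes review mandatory, not any route to review. Most Grade 4 events would reach the STRC, so the gap is narrow.

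The untested-dose argument also has limits. Each fallback is a step down from a failed level. On the 1,700 path the dose lies between 1,200 mg/m²/day with 0/3 DLTs and 2,300 mg/m²/day, which failed. The 600 mg/m²/day fallback is justified in the text as a weekly total equal to the single-dose MTD.

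Finally, Section 9.0 says the scheme was discussed with or proposed by the FDA, and an uncounted expansion cohort in a descriptive pilot is a design choice. That raises the cost of a change. It does not explain why five cohorts have a fixed count and the largest has none.

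**Conclusion.** The point holds in this limited form: no DLT count in Cohort 5 requires a review, and the existing safeguards leave related Grade 3 and expected Grade 4 events able to accumulate without one. It should be fixed, but it does not invalidate the trial.

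The size depends on assumed DLT rates. At 30-40%, a level once reached clears with probability 0.49-0.31, and the full rule would then pause Cohort 5 with probability 0.62-0.81, after about 7 to 6 patients on average rather than 10. At 10% it would seldom act. The clear-then-pause figures describe one level followed by Cohort 5. A reader might take them as the risk for the whole trial, but they do not model the path through Cohorts 2-4. Patients treated before review are not patients spared, since reviewers may resume enrolment. The 1,700 mg/m²/day path adds weight only if the Cohort 2 rule prevails over the conflicting Cohort 3 opening condition.

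**What to change.** In 6.1.1 and 9.0, state that DLTs are counted in Cohort 5 through Cycle 1. State also that enrolment pauses for review by the drug sponsor and the STRC at 2 DLTs within the first 6 patients, 3 within 7-8, or 4 within 9-10, with the dose decision left to the reviewers. The first limit is the plan's own; the later two are one reasonable choice, and the team may set others. Report the Cohort 5 DLT proportion with its exact 95% interval (for example 1/10: 0.3% to 44.5%; 4/10: 12.2% to 73.8%).

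The cost is one paragraph in two places and an amendment to a scheme discussed with the regulator. No extra patients or forms are needed, because the Appendix C log already has a DLT field. The downside is some delay at one patient per month, with a pause in about 12% of trials at a true rate of 10% and 37% at 20%. Whether the latter is unneeded depends on the rate the team would tolerate, which the plan does not state.

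Separately, use one DLT definition in all cohorts. Section 6.1.1 requires probable or definite attribution to CPI-613, while 9.0 counts any toxicity of Grade 3 or higher, so the same events can lead to different dose decisions. Because 9.0 says it repeats 6.1, align it to 6.1.1. That version is the less conservative of the two, so the sponsor should confirm it.

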6.1 Dose Levels, Dose Escalation, Sample Size and Justification of the Dose

6.1.1 Dose Levels, Dose Escalation and Sample Size

The dose levels to be used in assessing the safety and anti-cancer activities of CPI-613 in 10 patients with advanced bile duct cancers will be determined from a dose-escalation scheme using cohorts of patients with advanced bile duct cancers, as described below. The dose-escalation scheme is based on the number of patients exhibiting dose-limiting toxicity (DLT), and DLT is defined as toxicity of Grade 3 or higher attributed as probably or definitely related to CPI-613. The DLT determining period for all cohorts in the dose-escalation scheme is through the first cycle.

Comprehensive Cancer Center of Wake Forest University
A Pilot Study: Open-Label Clinical Trial of CPI-613 in Patients with Advanced Bile Duct
Cancers
CCCWFU # 59212

Cohort 1: The first 3 patients will not be treated with the 5 daily doses of CPI-613 during the pre-Cycle 1 week, and will only be treated with 3-weeks-on-1-week-off treatment cycles (see Table 6-1). The dose of CPI-613 will be 2,300 mg/m² (which is approximately three-quarters of the target dose). If none of these 3 patients develop a dose-limiting toxicity (DLT) through Cycle 1, the dose for the 3-weeks-on-1-week-off treatment cycles will be 3,000 mg/m² in all subsequent patients in this trial. However, if a DLT is observed in a patient (whether it is the 1st, 2nd or 3rd of the 3 intended patients), the number of patients in this cohort will be expanded to a maximum of 6 patients. If no DLT is observed in another patient out of a maximum of 6 patients, the dose for the 3-weeks-on-1-week-off treatment cycles will be 3,000 mg/m² in all subsequent patients in this trial. However, once DLT is observed in 2 patients, no additional patients will be treated at 2,300 mg/m² for the 3-weeks-on-1-week-off treatment cycles from that point on, even though the total number of patients in this cohort is as few as 2. The dose level of 2,300 mg/m², which induces a DLT in 2 or more patients, is considered to be above the maximum tolerated dose (MTD) for the 3-weeks-on-1-week-off treatment cycles. In this case, all subsequent patients in this trial will be treated at 1,700 mg/m² for the 3-weeks-on-1-week-off treatment cycles.

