9.0 STATISTICAL CONSIDERATIONS

This is a pilot study with the primary goal to be able to determine initial estimates of RR, and secondary goals to determine PFS and OS. Data from this trial will also provide additional data concerning the safety profile of the CPI-613 therapy. Since there is some uncertainty about what dose to examine for the 10 patients in this pilot study we propose the following pre-defined dose escalation scheme in order to determine the appropriate dose to provide to 10 patients with advanced bile duct cancers. This scheme has been discussed/proposed by the FDA and it is very specific and is described below. The dose-escalation scheme is based on the number of patients exhibiting dose-limiting toxicity (DLT), and DLT is defined as toxicity of Grade 3 or higher. The DLT determining period for all cohorts in the dose-escalation scheme is through the first cycle. Note – this section is redundant with section 6.1 but is included for completeness.

Cohort 1: The first 3 patients will not be treated with the 5 daily doses of CPI-613 during the pre-Cycle 1 week, and will only be treated with 3-weeks-on-1-week-off treatment cycles (see Table 6-1). The dose of CPI-613 will be 2,300 mg/m² (which is approximately three-quarters of the target dose). If none of these 3 patients develop a dose-limiting toxicity (DLT) through Cycle 1, the dose for the 3-weeks-on-1-week-off treatment cycles will be 3,000 mg/m² in all subsequent patients in this trial. However, if a DLT is observed in a patient (whether it is the 1st, 2nd or 3rd of the 3 intended patients), the number of patients in this cohort will be expanded to a maximum of 6 patients. If no DLT is observed in another patient out of a maximum of 6 patients, the dose for the 3-weeks-on-1-week-off treatment cycles will be 3,000 mg/m² in all subsequent patients in this trial. However, once DLT is observed in 2 patients, no additional patients will be treated at 2,300 mg/m² for the 3-weeks-on-1-week-off treatment cycles from that point on, even though the total number of patients in this cohort is as few as 2. The dose level of 2,300 mg/m², which induces a DLT in 2 or more patients, is considered to be above the maximum tolerated dose (MTD) for the 3-weeks-on-1-week-off treatment cycles. In this case, all subsequent patients in this trial will be treated at 1,700 mg/m² for the 3-weeks-on-1-week-off treatment cycles.

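### A possibly related Grade 3–4 renal event is not a DLT under Section 6.1.1 but is one under Section 9.0, and Section 6.2 acts on it without linking it to the cohort's DLT count

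*Combined protocol and SAP*

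**What the plan says.** Three sections of the combined protocol and SAP bear on this.

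- **Section 6.1.1** sets the escalation rule. It states that "DLT is defined as toxicity of Grade 3 or higher attributed as probably or definitely related to CPI-613", and that "The DLT determining period for all cohorts in the dose-escalation scheme is through the first cycle". Section 8.1 lists Possible as a separate category below Probable and Definite, so a possibly related event falls outside this definition.
- **Section 9.0** restates the scheme and says of itself that "this section is redundant with section 6.1 but is included for completeness". Its definition reads "DLT is defined as toxicity of Grade 3 or higher. The DLT determining period for all cohorts" and so on. It sets no attribution condition.
- **Section 6.2** sets dose modification. For Grade 3 or 4 toxicity in general, the trigger is a probable relation. For renal toxicity it is lower: "For adverse events related to creatinine elevation or reduction in renal function that are possibly related to CPI-613, dosing of the patient will be withheld", with a 50% reduction at Grade 3 or 4. In addition, "if the toxicity possibly related to CPI-613 is acute renal failure and the severity level is Grade 3 or 4, further patient enrollment" is to be temporarily suspended. The suspension lists two aspects to assess: adherence of sites and investigators to the protocol, and "evaluation of the appropriateness of the procedures for monitoring renal function". The same sentence allows for corrective measures or a protocol amendment.

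**The concern.** Renal toxicity is the only organ toxicity with its own hold, reduction and enrolment-suspension rules, and those rules start at a possible relation. The plan does not settle whether an event at that level counts towards the decision to raise the dose. The answer depends on which of two sections is read, and the second section presents itself as a repeat of the first. Section 6.2 does not resolve this, because neither listed review aspect is the dose level or the cohort's DLT count.

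The DLT count fixes the dose for the 10 patients who form the analytic sample, and safety is a primary outcome (Section 2.2). Two teams following the same protocol could reach opposite escalation decisions on the same data. The report could then not say without qualification which rule produced the dose called the MTD.

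**Working it through.** The plan gives no figure on this point to reproduce. The check sets the rules side by side, applies them to the same cohort, and then illustrates the size with assumed rates.

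**1. The same event under each section.** Take a Grade 3 or 4 renal event within the DLT window, judged possibly related.

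| Section | Attribution needed | Result |
|---|---|---|
| 6.1.1 | probable or definite | not a DLT |
| 9.0 | none stated | DLT |
| 6.2 | possible | dosing withheld, dose cut by 50%; enrolment suspended if acute renal failure; no statement on the DLT count |

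**2. The cohort rule.** Both sections use the same counting rule: 0 DLTs in 3, proceed; 1 DLT, expand to a maximum of 6 and proceed if there is no second; 2 DLTs, the level is considered above the MTD. With no other DLT in a cohort of 3:

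| Patients with such an event | Read under 6.1.1 | Read under 9.0 |
|---|---|---|
| 1 of 3 | 0/3, proceed | 1/3, expand to at most 6 |
| 2 of 3 | 0/3, proceed | 2 DLTs, above the MTD |

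In Cohort 2 the path differs even if the expanded cohort has no second DLT, because 1 in 6 leads to Sub-Cohort 2 and not to Cohort 3.

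**3. Illustration.** Let p be the chance that a patient has such an event in the window, with patients independent and no other Grade 3 or higher toxicity. The values of p are assumptions. A cohort clears if it ends with fewer than 2 DLTs.

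- Under 6.1.1 the counted rate is 0, so P(clear) = 1 at any p.
- Under 9.0, P(clear) = (1−p)³ + 3p(1−p)² × (1−p)³.
 - p = 0.10: 0.729 + 0.177 = 0.906
 - p = 0.20: 0.512 + 0.197 = 0.709
 - p = 0.33: 0.301 + 0.134 = 0.434
- The two definitions already give different counts after the first three patients with probability 1 − (1−p)³ = 0.271, 0.488 and 0.699.

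**4. Allowing other DLTs.** Step 3 is the extreme case in which 6.1.1 counts nothing. Now let q be the rate of any Grade 3 or higher toxicity, and s the share of patients with such toxicity whose events are rated no higher than possible. Section 9.0 counts q and 6.1.1 counts q(1−s). The same formula gives:

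| q | 9.0 | 6.1.1, s = 0.25 | s = 0.50 | s = 0.75 |
|---|---|---|---|---|
| 0.20 | 0.709 | 0.814 | 0.906 | 0.973 |
| 0.33 | 0.434 | 0.605 | 0.783 | 0.933 |

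In this table the gap runs from 0.814 − 0.709 = 0.105 to 0.933 − 0.434 = 0.499. It covers all such toxicity, not only renal events.

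**5. Room for expansion.** There are five escalation cohorts (1, 2, Sub-Cohort 2, 3 and 4). At 6 patients each that is 5 × 6 = 30, and 30 + 10 = 40, which reproduces the maximum in Section 9.0.

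**The case against.** A reader might infer more: that under the plan as written such a cohort always counts as free of DLTs and the next dose opens. The documents do not support that.

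- Section 9.0 counts the event, so certain clearance holds only under 6.1.1.
- The event must fall in the window, with no other DLT in the cohort.
- Section 6.2 suspends enrolment so that corrective measures or an amendment can follow, and nothing bars these from addressing dose.
- In Cohorts 2 to 4 and Sub-Cohort 2, 0 DLTs in 3 means that the study can move on, not that it must. Only Cohort 1 is worded as automatic, and it sets the cycle dose.

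There is also other oversight. Under Appendix B, unexpected Grade 4 and all Grade 5 events go to the safety committee whatever their attribution, and the committee may suspend the trial. Under Section 8.1, possibly related unexpected SAEs go to the drug sponsor. These routes are partial: no Grade 3 event has to reach the committee, and creatinine is listed as expected, so neither does a Grade 4 creatinine elevation. The 6.2 suspension covers acute renal failure only.

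A lower threshold for protecting one patient than for judging a dose level can be a deliberate choice, so the difference between 6.1.1 and 6.2 is not in itself an error. That is a fair point. It does not explain why 6.1.1 and 9.0 differ, or why 6.2 is silent on the count.

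Finally, no document gives a rate for p, and Section 6.1.2 reports no significant adverse effects at or below the earlier MTD. The figures show how far the definitions can diverge; they do not predict what will happen.

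**Conclusion.** The conflict is real and can be read directly from the text. The same possibly related Grade 3 or 4 renal event leaves the count at zero under 6.1.1 and adds one under 9.0, while 6.2 treats it as serious enough to halve a dose or pause enrolment without saying how it counts. One such patient in three decides between moving on and expanding; two decide between moving on and a level above the MTD.

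Under the assumed rates of 0.10, 0.20 and 0.33, clearance is certain under 6.1.1 and 91%, 71% or 43% under 9.0. This assumes independent patients and no other Grade 3 or higher toxicity, and the gap is smaller where some events count under both definitions. The finding is that the outcome is undetermined. It is not that a dose would necessarily be cleared, and it does not say which threshold is right.

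**What to change.** Reconcile Sections 6.1.1, 6.2 and 9.0.

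- Give one DLT definition, identical in 6.1.1 and 9.0, or have 9.0 refer to 6.1.1 and not restate it.
- State explicitly how a possibly related Grade 3 or 4 renal event in the window enters the cohort's DLT count, including one that triggers the 6.2 suspension.
- If any cohort has already been assessed, record which definition was applied to it.

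Which threshold applies is for the sponsor and the investigator to decide. The cost is a few sentences in an amendment. Depending on the choice, some cohorts may expand from 3 to 6 patients, which stays within the stated maximum of 40 but lengthens accrual at the planned rate of one patient per month.
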